The MR5 Prototype Device is designed to provide pain relief and non-invasive treatment of diverse conditions. The device, which may be used in combination with pharmacological methodologies, operates in phototherapeutic modes providing simultaneous penetrative impact of coherent and incoherent light energy. These include infrared and visible red light and are delivered into biological tissues in combination with a surface impact provided by a static magnetic field. Phototherapeutic treatment is carried out by placing the light emitting aperture directly over the affected area according to the study protocol.

Figure 1: MR5 Prototype Device

Figure 2: The Multi Radiance Medical MR5 Prototype Device Technical

MR4 Prototype Settings				
Wavelength	905	850	660	905, 850, and 660
Total Power (Average, W)	0.001375	0.25	0.2	0.451375
Number of Diodes	1	3	3	7
Power per Diode (W)	0.001375	0.083333	0.066667	N/A
Irradiance W/cm2	0.000344	0.062500	0.050000	0.112844
Fluence J/cm2	0.020625	3.750000	3.000000	6.770625
Time Duration (seconds)	60			
Frequency of SPL (Hz)	250			
Laser Peak Pulse				
Power (W)	50			
Laser Pulse Duration (s)	0.00000011			
Aperture area (cm2)	4			
Laser average power (W)	0.001375			
IR average power (W)	0.25			
Red average power (W)	0.2			
Battery:				
Li-polymer battery Voltage.....	3,7			
Capacity, amp-hour.....	4			
Continuous operation with fully charged batteries, hours, no less.....	6			
Battery complete charging time, hours, no more	4			
Input voltage of power adapter for battery charging.....	100...240 VAC, 50/60 Hz			
Output voltage of power adapter.....	12,0 VDC			
Laser safety according to:				
IEC 60825-1:2007 and IEC 60825-1:2014	Class 1			
Electric classification by IEC 60601-1.....	battery powered device, type BF applied part			
Device Specifications:				
Overall dimensions, mm.....	203x64x70			
Net weight, g, no more (w/o adapter).....	250			
Average lifetime, years.....	5			
Operational Environment				
Temperature		Humidity		Atmospheric Pressure
40°C (104°F)		<80%		70-106 kPa
				
10°C (50°F)				
Storage/Transport Environment				
Temperature		Humidity		Atmospheric Pressure
45°C (113°F)		<80%		50-106 kPa
				
0°C (32°F)				

PURPOSE OF STUDY

The purpose of this multi-center clinical study is to determine the effectiveness of the Multi Radiance Medical MR5 Prototype Device manufactured by Multi Radiance Medical (the Company), MR5® Prototype Device for temporary adjunctive use to relieve pain associated with Lateral Epicondylitis.

STUDY DURATION

The estimated total duration of the study is four to five months.

LABELING

Once the device has been cleared for market in the U.S., the device will be labeled as a prescription device, per 21 CFR § 801.109.

PROPOSED INDICATIONS FOR USE

The indication (claim) being sought through support of the results of this clinical study is: "The Multi Radiance Medical MR5 Prototype Device is indicated for temporary adjunctive use to relieve pain associated with Lateral Epicondylitis." It is intended that the results of this clinical study be used to support a DeNovo submission to FDA for clearance to market the device for the intended indication.

EXPECTED RESULTS

Following completion of the study procedure protocol with the Multi Radiance Medical MR5 Prototype Device, it is anticipated that relative to baseline (pain at rest), significantly more subjects in the test group than in the placebo group will show a 30% or greater reduction in self-reported VAS rating in the Lateral Epicondylitis following completion of the three-week study procedure administration phase.

REGULATORY HISTORY

The MR4™ Multi Radiance Therapy and its various emitters and accessories have received the following 510(k) clearances from the United States Food and Drug Administration (FDA):

1. K080102

- *Device Name:* MR4™ Multi Radiance Therapy System, TQ Solo, TQ Solo Pro, and LS50 Accessory
- *Regulatory Class:* Class II
- *Product Code:* ILY, GEX
- *Clearance date:* August 20, 2008
- *Indications for Use:* All four devices are indicated for temporary relief of minor muscle and joint pain, arthritis and muscle spasm, relieving stiffness, promoting relaxation of muscle tissue, and to temporarily increase local blood circulation where heat is indicated.
- *Over-The-Counter (OTC) use*

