2. K171354

- *Device Name:* MR4™ Laser
- *Regulatory Class:* Class II
- *Product Code:* NHN
- *Clearance date:* January 13, 2018
- *Indications for Use:* MR4 Laser is indicated for adjunctive use in providing temporary relief of minor chronic neck and shoulder pain of musculoskeletal origin.
- *Prescription use*

TECHNOLOGY, LITERATURE, BACKGROUND, THEORY OF MECHANISM OF OPERATION, PRODUCT OVERVIEW & SAFETY

BACKGROUND:

LATERAL EPICONDYLITIS:

Upper extremity musculoskeletal disorders are common in the general population. These disorders may include diseases such as cervical disc disease, rotator cuff disease, lateral and medial epicondylitis, carpal tunnel syndrome, osteoarthritis, and other conditionsⁱ. Studies report that these disorders have a negative impact on quality of life^{ii, iii, iv}, since upper extremity pain can cause substantial disability, need for health care, and loss of work time^v. Among the most common upper extremity disorders are lateral and medial epicondylitis, which have been reported to significantly affect the upper extremity function, causing losses in daily living activities^{vi, vii}.

Lateral epicondylitis (LE) is one of the most frequently encountered lesions affecting the upper extremity and is the most common cause of elbow pain in adults. It occurs on the lateral side of the elbow where the common extensors originate from the lateral epicondyle^{viii, ix, x}. It is defined as an injury involving the wrist common extensor tendons, particularly the carpi radialis brevis and extensor digitorum^{xi}. LE is a common term used to describe a group of symptoms, including pain and tenderness over the origin of extensor muscles of the wrist and fingers, and is also known as tennis elbow, as it is frequently seen in racquet sports players^{xii, xiii, xiv, xv}. This clinical condition has a significant impact on the healthcare industry and society in general^{xvi, xvii}.

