After 50+ years of low intensity level light applications in humans with lasers (or any other optical to near infrared light sources) there are no known reports of any adverse side effects to the best of our knowledge.^{lxxxv} The MR4™ Laser Therapy System and many other light devices are cleared (FDA, Health Canada, TGA) and considered safe for both professional and consumer home use (OTC). Low level laser devices have been designated by FDA as non-significant risk. Multi Radiance® Medical also complies with ISO 13485 Certification to ensure good manufacturing practices for consistency in product quality, monitoring and reporting.

The Multi Radiance Medical Super Pulsed Infrared Laser (905 nm) in the ACTIV PRO creates the desired higher peak power, however due to the ultrashort pulses, there is little resulting heat accumulating within the target tissue. Vanin, et al.^{lxxxvi} replicated a study by Grandinétti, et al.^{lxxxvii} that evaluated the thermal impact of the MR5 Prototype Device on light, medium and dark skin. Baseline measurements were taken prior to the start and skin temperatures were measured using a FLIR thermographic camera. Four doses were applied: placebo, 25 J, 80 J, and 133 J to the skin. The MR5 Prototype Device was set to full power (500 mW and 50 Hz frequency).

	Light	Intermediate	Dark
Baseline	33.84	34.74	34.48
72 sec	34.28	34.86	34.90
228 sec	34.54	35.45	35.21
380 sec	35.54	36.46	36.06

There was a non-significant increase ($p>0.05$) in temperature (degrees C) for all skin types and with all doses. No groups experienced excessive photothermal effects that may affect patient safety and no threat or concern regarding cytotoxicity in clinical practice exists. The lack of accumulating skin temperature may be attributed to the ultra-short pulse structure related to the frequency of the super pulsed laser and pulsing of the LEDs and IREDS.

DEVICE SAFETY

RISK AND PREVENTION OF EYE INJURY

The MR5 Prototype Device - This product is classified as Class 1 according to EN IEC 60825-1:2007. Access to laser radiation in excess of Class 1 is not possible during normal operation, and/or maintenance functions.

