Subjects will be recruited from three different sites and among the licensed health care provider's test site's pool of patients who are currently being treated for, or who are seeking treatment for Lateral Epicondylitis, or from patients who respond to the following recruitment materials, if needed.

Flyer

WANTED

ADULTS WITH LATERAL EPICONDYLITIS, ONGOING
FOR ONE MONTH, FOR A CLINICAL STUDY
OF THE EFFECTS OF LOW-LEVEL LASER LIGHT ON REDUCING LATERAL
EPICONDYLITIS.

**THIS STUDY INVOLVES SIX LASER LIGHT PROCEDURES, TWO TIMES A WEEKS FOR
THREE WEEKS WITH THE MULTI RADIANCE MEDICAL® MR5® LASER AT THE TEST
SITE.**

THERE IS THREE VISITS PRIOR TO LASER LIGHT PROCEDURES WITH ONE MORE
VISIT TO THE TEST SITE
ONE MONTH AFTER THE LAST LASER LIGHT PROCEDURE.

YOU WILL RECEIVE \$450 IF YOU FINISH THE STUDY.

FOR MORE INFORMATION PLEASE CONTACT:

<PI name>
<test site name & location>
<phone # and/or e-mail>

Newspaper Ad

**Lateral Epicondylitis
Research Study**

This study is to see if the Multi Radiance Medical® MR5® LASER, a non-invasive, investigational device that uses low-level laser light, can help to relieve symptoms of Lateral Epicondylitis pain longer than one month in duration.

The study involves ten visits to a test site and recording some information at home.

You will receive \$450 if you finish the study. Please contact
<PI name> at
<test site name & location> at
<phone and/or e-mail> for details.

Compensation

A subject will be paid a stipend of \$450.00 USD for their participation in the study upon completion. Subjects will not be charged for the cost of the study procedures administered with the Multi Radiance Medical® MR5® Prototype Device for the cost of any other directly related evaluations or measurements that occur as part of his or her participation in the study.

Sample size

There will be 60 subjects evaluated for eligibility in this clinical study:

- 30 subjects in the active procedure group
- 30 subjects in the control procedure group (Placebo)

Rationale for sample size

Based on the following parameters established for the purposes of assessing efficacy of the Multi Radiance Medical MR5 Prototype Device in this clinical study using the Fischer's Exact test to assess the primary endpoint.

- Individual subject success criteria is defined as a 30% or greater reduction in self-reported Degree of Pain rating on the 0-100 VAS from baseline to study endpoint evaluation.

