- Subject is willing and able to maintain his or her current pre-study Lateral Epicondyle pain management regimen of pain relief medication and/or treatment/therapy use throughout the course of study duration, whilst refraining from consuming other OTC and/or prescription medication(s) and/or herbal supplements intended for the relief of pain and/or inflammation, including muscle relaxants, and/or partaking in other treatments/therapies including conventional therapies such as physical therapy, occupational therapy and hot or cold packs, as well as alternative therapies such as chiropractic care and acupuncture.
- 18 years of age or older
- Male or female
- Subject is fluent in Portuguese

EXCLUSION CRITERIA

A subject who satisfies any of the following criteria will be excluded from study participation:

- hemophilia or any type of blood clotting disorder
- chronic immune impairment neoplasia
- neurologic deficits
- cervical radiculopathy
- peripheral nerve disease
- rheumatoid arthritis
- shoulder disease
- radial tunnel syndrome
- previous surgery of the affected upper extremities
- congenital or acquired bony deformity in the ipsilateral upper extremity
- the initiation of opioid analgesia or corticosteroid or analgesic injection interventions within the previous 6 months

- physical therapy intervention on the upper extremity in the previous year
- bilateral epicondylitis
- secondary orthopedic problems.

Physical Examination of the Lateral Epicondyle Region:

- Lateral Epicondyle pain is acute, defined as having persisted over less than the last 1 month
- Self-reported Degree of Pain rating on the 0-100 VAS pain scale for the Lateral Epicondyle region is less than 50
- Local corticosteroids and/or botulinum toxin (Botox®) injection for Lateral Epicondyle pain relief within the prior 30 days
- Medical tx; such as chiropractic care and acupuncture within last 30 days
- Current, active chronic pain disease: chronic fatigue syndrome, fibromyalgia, endometriosis, inflammatory bowel disease, interstitial cystitis diabetic neuropathic pain
- Cancer or treatment for cancer in the past 6 months, including tumors of the spinal cord
- Diabetes Type 1
- Significant heart conditions including CHF and implantable heart devices such as a pacemaker
- Active infection, wound, or other external trauma to the areas to be treated with the laser
- Medical, physical, or other contraindications for, or sensitivity to, light therapy

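### Light therapy already in use on the affected elbow is neither excluded nor removed from the regimen that subjects must keep

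*Combined protocol and SAP*

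**What the plan says.** **Availability.** Under Regulatory History, the K080102 entry covers the MR4 system and three related products. It says "All four devices are indicated for temporary relief of minor muscle and joint pain" and lists them for "Over-The-Counter (OTC) use". The Safety section says that the MR4 system and many other light devices are cleared by FDA, Health Canada and TGA and "considered safe for both professional and consumer home use (OTC"). The second entry, K171354, is a prescription clearance.

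**Recruitment.** Under Subjects, Recruitment, subjects come from each site's "pool of patients who are currently being treated for, or who are seeking treatment for Lateral Epicondylitis", or through advertisements.

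**Regimen.** The inclusion criteria require that the subject can "maintain his or her current pre-study Lateral Epicondyle pain management regimen of pain relief medication and/or treatment/therapy use throughout the course of study duration". The same item bars other pain medicines and other treatments or therapies, with physical therapy, hot or cold packs, chiropractic care and acupuncture among its examples. No modality is carved out of the regimen to be kept.

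**Exclusions.** The only line that names light therapy is "Medical, physical, or other contraindications for, or sensitivity to, light therapy". Two further lines could touch it: physical therapy on the upper extremity in the previous year, and an open-ended line on medical treatment within 30 days, with chiropractic care and acupuncture as its examples.

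**Data collected.** Under Pre-Procedure Variables, baseline and historical treatment or therapy use are recorded. No rule in the text acts on a report of light therapy.

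**The concern.** The trial compares light with no therapeutic light. The criteria restrict several competing treatments but are silent on use of the modality under test. A subject who self-applies a light device at home meets the criteria, is told to keep the regimen, and can be randomised to either arm. In the placebo arm that subject is not free of light therapy. In the active arm the study device is added to light therapy already in use. Either way the subject says little about light against no light.

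The overall success criterion is a 30-point difference in responder proportions, and the planned rates of 50% and 20% give exactly 30 points. Any dilution therefore takes the expected difference below the criterion.

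**Working it through.** **1. Who can be on light therapy, reading the criteria together**

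| Situation | What the text does |
|---|---|
| Starts light therapy during the study | Barred as another treatment or therapy |
| Clinic-delivered, given as physical therapy within a year | Probably excluded by the physical-therapy line |
| Clinic-delivered within 30 days, outside physical therapy | Possibly excluded by the open-ended medical-treatment line |
| Self-applied home device, already in use at entry | Not excluded; part of the regimen to be kept |
| Home use that ended before entry | Not excluded |

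The clear gap is the fourth row. Recent past use (fifth row) is also unaddressed.

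**2. The plan's own sample-size figure**

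Inputs from Rationale for Sample Size: 50% versus 20%, two-sided alpha 0.05, power 0.80, 25 per group. The usual formula is

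n = [1.96·√(2·0.35·0.65) + 0.8416·√(0.5·0.5 + 0.2·0.8)]² / 0.30² = (1.322 + 0.539)² / 0.09 ≈ 38.5, so 39 per group, or 45 with continuity correction.

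The stated 25 is not reproduced. This is a separate matter, but it sets the starting point: exact power of the two-sided Fisher test at 25 per group is 51.0% before any dilution.

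**3. Expected difference with users present**

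Let c be the share of subjects in each arm who already use light therapy, and d the responder difference that the study device makes among them. Non-users keep the planned 0.30. Then

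difference = 0.30·(1 − c) + c·d.

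If d = 0.30 nothing is lost. If d = 0 the difference is 0.30·(1 − c), whatever the users' common response rate. Neither c nor d is in the documents. The values below are assumptions: d = 0 and c = 5%, 10% or 20%. At 25 per arm these shares are 1.25, 2.5 and 5 subjects.

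**4. Power**

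Power is the sum, over all pairs of responder counts for which two-sided Fisher p ≤ 0.05 in favour of active, of the product of the two binomial probabilities (n = 25 each). Two versions of d = 0 are shown.

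- Version A: users respond at 20% in both arms, so the active rate is 0.50 − 0.30c and placebo stays at 0.20.
- Version B: users respond at 50% in both arms, so placebo is 0.20 + 0.30c and active stays at 0.50.

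| c | Difference (points) | A: active rate | A: power | B: placebo rate | B: power |
|---|---|---|---|---|---|
| 0 | 30 | 50% | 51.0% | 20% | 51.0% |
| 5% | 28.5 | 48.5% | 46.5% | 21.5% | 46.3% |
| 10% | 27 | 47% | 41.9% | 23% | 41.6% |
| 20% | 24 | 44% | 33.3% | 26% | 33.1% |

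Version A fits the design better. Baseline is taken on the maintained regimen, and the Continued Study Eligibility Evaluation requires a three-day average VAS of 50 or more. The effect of a device already in use is therefore largely in the baseline, and a continuing placebo user has no evident reason to respond at the active rate.

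**The case against.** **Dilution does not fit the endpoint.** Success is a 30% fall from a baseline recorded on the existing regimen, and a subject whose home device works well would not average 50 or more. This stands against the idea that placebo users would respond at 50%. It does not remove the dilution: subjects with inadequate relief on light therapy may gain less from more light, which lowers the active rate instead.

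**The size is assumed.** This stands. No usage rate is given. The over-the-counter status rests on FDA, Health Canada and TGA clearances, while subjects must be fluent in Portuguese, so availability to the people recruited is not shown.

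**The list is not closed.** This stands in part. The two lines noted above may catch clinic-delivered light therapy. Neither names it, and neither clearly reaches a self-applied device.

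**It is handled in analysis.** Therapy history is recorded, the investigator reviews regimen use before treatment starts, and use of regimen components enters an ANCOVA and a regression. But those analyses take any component together and rely on use during the study. They do not restore a light-versus-no-light contrast in the primary Fisher test. Appendix C, cited for medication regimen details, is not in the text available and might address the point.

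**Two stronger readings.** A reader might infer that earlier users would recognise the sham. The Subject Groups and Triple Blind Design sections describe the devices as indistinguishable in appearance and visible light, with no notable heat or noise. No passage supplies a cue that experience with another device would reveal, and perceived assignment is collected and analysed. A reader might also infer bias in favour of the device. Randomisation would be expected to spread users over both arms, so the expected effect is dilution.

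**Conclusion.** The gap is real and narrow. The criteria permit light therapy already in use on the affected elbow, and the regimen item requires it to continue in either arm. The exposure that clearly gets through is self-applied use that predates entry.

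Each 10% of such users costs 3 points of expected difference, on the assumptions that users are equally common in both arms and gain nothing further from the study device. At 25 per arm, Fisher power falls from 51% to about 46%, 42% or 33% for 5%, 10% or 20% users. If the study device does help them, the loss is smaller. The true share is unknown and could be close to zero. The shortfall from 80% to 51% comes from the sample size and should not be attributed to this point.

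This is an inexpensive improvement to the criteria. The documents do not show that the trial's result would be compromised.

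**What to change.** Add to the Exclusion Criteria: current or recent laser, LED or other light treatment of the affected elbow, whether clinic-delivered or over the counter, within a look-back that the sponsor sets. Ask about it at screening, by bringing forward the treatment and therapy history that Pre-Procedure Variables already collects, so that the answer is known before randomisation. If Appendix C already deals with light therapy, carry that statement into the eligibility section so that the two agree.

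The cost is one eligibility sentence, one screening question and a few more screen failures. No change to the analysis is needed.

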2. K171354

- *Device Name:* MR4™ Laser
- *Regulatory Class:* Class II
- *Product Code:* NHN
- *Clearance date:* January 13, 2018
- *Indications for Use:* MR4 Laser is indicated for adjunctive use in providing temporary relief of minor chronic neck and shoulder pain of musculoskeletal origin.
- *Prescription use*

TECHNOLOGY, LITERATURE, BACKGROUND, THEORY OF MECHANISM OF OPERATION, PRODUCT OVERVIEW & SAFETY

BACKGROUND:

LATERAL EPICONDYLITIS:

Upper extremity musculoskeletal disorders are common in the general population. These disorders may include diseases such as cervical disc disease, rotator cuff disease, lateral and medial epicondylitis, carpal tunnel syndrome, osteoarthritis, and other conditionsⁱ. Studies report that these disorders have a negative impact on quality of life^{ii, iii, iv}, since upper extremity pain can cause substantial disability, need for health care, and loss of work time^v. Among the most common upper extremity disorders are lateral and medial epicondylitis, which have been reported to significantly affect the upper extremity function, causing losses in daily living activities^{vi, vii}.

Lateral epicondylitis (LE) is one of the most frequently encountered lesions affecting the upper extremity and is the most common cause of elbow pain in adults. It occurs on the lateral side of the elbow where the common extensors originate from the lateral epicondyle^{viii, ix, x}. It is defined as an injury involving the wrist common extensor tendons, particularly the carpi radialis brevis and extensor digitorum^{xi}. LE is a common term used to describe a group of symptoms, including pain and tenderness over the origin of extensor muscles of the wrist and fingers, and is also known as tennis elbow, as it is frequently seen in racquet sports players^{xii, xiii, xiv, xv}. This clinical condition has a significant impact on the healthcare industry and society in general^{xvi, xvii}.

LE can be considered an overuse injury which occurs on the lateral side of the elbow in the extensor tendons with repetitive micro-trauma^{xviii, xix}. It typically presents around the lateral epicondyle elicited by forced wrist extension, this is the result of the degenerative angiofibroblastic hyperplasia of wrist extensor tendons due to repeated micro-traumas^{xx, xxi}. This condition is usually related to repetitive occupations or hobbies^{xxii}. Besides overuse and repetitive movements, other relevant risk factors include wrong training, misalignment, flexibility problem, age, poor circulation and muscle weakening or imbalance^{xxiii, xxiv}. While the exact pathophysiology behind the condition is not yet clear, and despite the presence of inflammatory cells locally, there are arguments that LE can be regarded as a degenerative process caused by muscle overuse, with subsequent tendinosis, microtrauma and tear of the extensor carpi radialis tendon^{xxv, xxvi}.

The prevalence rate of LE is more than 1% in the general population, with a slight predominance among females^{xxvii, xxviii}. It is commonly seen in racquet sports players with a reported incidence of 9 ~ 35% and prevalence of 14 ~ 41% among tennis players^{xxix}. The disease mostly affects people between the ages of 35 – 50 years, who have a history of repetitive activities involving the upper limbs, and the dominant upper limb is much more often involved^{xxx, xxxi, xxxii}. The high prevalence of LE leads to a significant socioeconomic burden^{xxxiii}. Diagnosis is usually based on clinical history and physical examination, for a differential diagnosis, multiple exams can be used including simple radiography, ultrasonography, magnetic resonance imaging and electrodiagnosis^{xxxiv}.

The clinical presentation of LE involves a painful or burning sensation over the humeral insertion of the common extensor tendons^{xxxv}. This pain can be exacerbated by wrist extensor activation, passive wrist flexion combined with passive elbow extension^{xxxvi}, and palpation over the lateral epicondyle or the origin of the wrist extensor muscle groups^{xxxvii}. People affected by LE in the lateral epicondyle show increased pain and decreased functional abilities due to the weakening of the rotator cuff and the scapula muscular

systems^{xxxviii}. They will commonly present with a loss of grip strength and usually report pain during daily activities such as grasping objects, turning doorknobs and shaking hands^{xxxix, xl}. In some cases, the recovery phase can take several months, potentially impacting the quality of life and sports performance of these individuals^{xli, xlii}.

Despite the high incidence of LE, optimal treatment has not been established, and, although treatments are usually non-surgical, such as oral medications, physiotherapy and corticosteroid injection, surgical decompression has been used to treat LE^{xliii}. The relatively large number of options currently available for LE treatment could be attributed to the scarce evidence available about the disease etiology and the lack of agreement about definitive treatment for the condition^{xliv, xlv, xlvii}.

Medial epicondylitis (ME) of the elbow is less commonly encountered than the lateral disease but is also a common pathology^{xlvii, xlviii, xlix}. The relative incidence of ME is 9.8% to 20%^{l, li}, and is often referred to as "golfer's elbow," because in the golf swing significant tension is noted across the medial aspect of the elbow^{li, lli}. However other activities involving repetitive use have also been implicated, they include tennis, swimming, weightlifting and work-related activities^{liv}. With the continuation of sport practice and active use of the elbow in the aging population, it has been diagnosed with increasing frequency^{lv}.

The underlying etiology of ME is described as an angiofibroblastic tendinosis in the origin of the common flexor-pronator, it has also been characterized as a micro-tearing in the origin of the flexor mass^{lvii}. It occurs due to repetitive forced wrist extension and forearm supination during activities involving wrist flexion and forearm pronation causing flexor-pronator tendon degeneration. The confluence of the flexor carpi radialis and pronator teres is frequently a common site of injury^{lvii}. A staged process of pathologic change in the tendon can result in structural breakdown and irreparable fibrosis or calcification^{lviii}.

Patients typically report persistent medial-sided elbow pain that is exacerbated by daily activities, it is usually present with flexion of the wrist and fingers and pronation of the forearm^{lix, lx}. The ME is primarily a condition of the middle aged, most injuries are degenerative in nature, but in some cases an acute trauma may precipitate the symptoms. Once the acute symptomatology is alleviated, focus is turned to flexor-pronator mass rehabilitation and injury prevention^{xi}.

Treatment of ME is initiated with nonsurgical modalities, this supportive care includes activity modification, physical therapy, oral medications and corticosteroid injections^{lxii}. Conservative treatment has been shown to relieve the pain, however this may depend on the stage of presentation. Surgical treatment via open techniques is typically reserved for patients with persistent symptoms, typically after at least six months of nonsurgical care^{lxiii}.

Considering the importance and high incidence of these musculoskeletal disorders, LE and ME, a variety of therapeutic modalities has been employed in order to alleviate pain and repair the tissue. Treatment options include therapeutic exercise, bracing, shock wave or ultrasound therapy^{lxiv}, but many of them lack sufficient evidence of beneficial effects^{lxv, lxvi}. The corticosteroid injections are often used but with limited success^{lxvii}. Photobiomodulation therapy (PBMT) has been shown to stimulate tendon healing, this suggests that therapy using laser or light-emitting diodes (LEDs) is efficacious for the symptoms associated with chronic epicondylitis^{lxviii}.

The PBMT was first used to target soft tissue inflammation and injuries, its applications have expanded to a multitude of musculoskeletal injuries, including tendon injuries^{lxix}. PBMT can

be performed using lasers or LEDs and is possible over a range of wavelengths, studies have demonstrated favorable results using PBMT on the tendon repair process, evidenced by improved quality of remodeling and decreased inflammation^{lxx, lxxi, lxxii, lxxiii}.

The PBMT is non-thermal, thus its effects are related to photochemical and photobiological effects within the tissue and not to heat^{lxxiv}. It is non-invasive, therapeutically beneficial and promotes a wide range of biological effects including the enhancement of energy production, gene expression and cell death prevention^{lxxv}. The major intracellular molecule absorbing photons is cytochrome c oxidase, an enzyme present in mitochondria, which can be stimulated by PBMT^{lxxvi}. So the PBMT modulates biological processes of cells in the mitochondrial level increasing oxygen consumption and production of adenosine triphosphate (ATP)^{lxxvii}. The PBMT also has the advantage of not having severe side effects.

Favorable results of PBMT in the tendon repair process have already been demonstrated, it promotes the deposition of collagen fibers in the early and late stages and minimization of inflammatory cells in the lesion area^{lxxviii, lxxix}. These beneficial outcomes of PBMT can be attributed to the modulatory effect of fibroblast metabolism and collagen deposition by matrix metalloproteinases, and activation or inhibition of inflammatory mediators. This also supports the indications that PBMT treated tendons have a higher turnover rate of collagen and higher mechanical integrity when compared to non-treated tendons^{lxxx}.

Epicondylitis (lateral or medial) has a significant impact on the health care system and society in general^{lxxxi}. Therefore, investigating the mechanisms involved in tendon repair in order to encourage the development of novel therapies for epicondylitis treatment is very important. According to the favorable results of PBMT in tendons repair processes, this type of therapy can be used as a therapeutic tool for management in epicondylitis, therefore, more investigations are necessary to establish the ideal parameters. With this in mind, we believe that PBMT, in the appropriate parameters, can significantly decrease pain and improve quality of life of patients presenting epicondylitis diagnosis.

THEORY OF MECHANISM OF OPERATION

The scientific principle underlying laser physics was first developed by Albert Einstein in 1916. The biological effects of low-level laser therapy (LLLT) have been studied globally for over forty years with no unwanted side effects noted.

General Therapeutic Effects and Mechanism of Operation of Low Level Lasers

“Low-energy photon irradiation by low level laser light lasers or LED arrays has been found to modulate various biological processes in cell culture and animal models. This mechanism of photobiomodulation by LLLT lasers or LED arrays at the cellular level has been ascribed to the activation of mitochondrial respiratory chain components, resulting in initiation of a signaling cascade that promotes cellular proliferation and cytoprotection.”

Source: Proc Natl Acad Sci U S A. 2003 Mar 18; 100(6): 3439-44. 2003 Mar 07.

L.A.S.E.R. (Light Amplification by Stimulated Emission of Radiation) is a name for a type of intense radiation of the light spectrum. A laser is a beam of light in which high energies can be concentrated. Laser light has unique physical properties of coherence and monochromaticity that other types of light do not have. It is these physical properties that make laser light so effective compared to other kinds of light in the field of pain reduction and healing. When applied to injuries and lesions, low level laser light has been shown to stimulate healing and reduce pain by accelerating the speed, quality and strength of tissue repair and the reduction of inflammation. Laser therapy has been found to be particularly

MR5® Prototype Device for temporary adjunctive use to relieve pain associated with Lateral Epicondylitis.

effective over other standard therapies in relieving pain and other symptoms associated with chronic problems and injuries as it impacts the complete system of targeted muscles, tendons, ligaments, connective tissue, bone, nerve, and dermal tissues.

The effects of low-level laser treatments are photochemical. Photons enter the tissue and are absorbed in the cell's mitochondria and at the cell membrane by chromophores. These chromophores are photosensitizers that generate reactive oxygen species following irradiation thereby influencing cellular redox states and the mitochondrial respiratory chain. Within the mitochondria, the photonic energy is converted to electromagnetic energy in the form of molecular bonds in ATP (Adenosine Triphosphate). In order to interact with the living cell, laser light has to be absorbed by intracellular chromophores. Cell membrane permeability increases, which causes physiological changes to occur. These physiological changes affect macrophages, fibroblasts, endothelial cells, mast cells, and bradykinin and nerve conduction rates. The clinical and physiological effects are obtained by the way in which tissues absorb laser radiation. This tissue absorption depends on the wavelength of the beam itself and the power to ensure that the laser energy reaches the target tissue at the necessary clinical levels. The improper wavelength of laser light would not penetrate into the tissue to reach the target area. Furthermore, even if one has a laser with the proper wavelength, if the device does not have enough power to drive the energy into the tissue, the target area may not realize the potential benefits. Each type of laser emits light at a very specific wavelength which interacts with the irradiated tissue. It also acts in particular with the chromophores present in the tissue, but in a different way. A chromophore, intrinsic or extrinsic, is any substance, colored or clear, which is able to absorb radiation. Among the endogenous chromophores are water and hemoglobin, nucleic acid and proteins. Among the exogenous chromophores are porphyrins and hematoporphyrins, which are injected into the organism. These are described as photosensitizers because they fix themselves to the tissue making it photosensitive at specific wavelengths.

The level of tissue penetration by the laser beam depends on the beam's optical characteristics, as well as on the concentration and depth of the chromophores, which are absorbed at different percentages according to the laser light's wavelength. For instance, water absorbs almost 100 percent of the laser irradiation at 10,600 nanometers, the wavelength of a CO₂ gas laser. That is the reason why this type of laser wavelength is used in surgical applications. Other factors affecting the depth of penetration are the technical design of the laser device and the particular treatment technique used. There is no exact limit with respect to the depth penetrated by the light. The laser light gets weaker the further from the surface it penetrates where eventually the light intensity is so low that no biological effect from it can be measured. In addition to the factors mentioned, the depth of penetration is also contingent on tissue type, pigmentation and foreign substances on the skin surface such as creams or applied oils. Bone, muscles and other soft tissues are transparent to certain laser lights, which means that light can safely penetrate these tissues. The radiation in the visible spectrum, between 400 and 600 nanometers, is absorbed by the melanin, while the whole extension of the visible which goes from 420 to 750 nanometers is absorbed by composite tetrapyrrols. In the infrared, which covers about 10,000 nanometers of light spectrum, water is the main chromophore. Fortunately, there exists a narrow band in the light spectrum where water is not a highly efficient chromophore, thereby allowing light energy to penetrate tissue that is rich in water content. This narrow band, which extends approximately from 600 to 1,200 nanometers, is the so-called "therapeutic window" and is the range within which the output design of the Multi Radiance Medical® MR5® Prototype Device is based.

In general, laser diodes are either continuous wave or pulsed. Continuous wave (CW) diodes emit laser energy continuously while pulsed diodes emit a radiation impulse with a high

